9.1.5 Response Review

All MR images will be reviewed by two blinded readers.

The results of both readers will be included in data and statistical analysis. Inter-reader agreement will also be evaluated by K statistics.

10. REGULATORY CONSIDERATIONS

10.1 Monitoring plan

The Stanford Cancer Center Data and Safety Monitoring Committee (DSMC) will be the monitoring entity for this study. The DSMC will audit study-related activities approximately once per year to determine whether the study has been conducted in accordance with the protocol, local standard operating procedures, FDA regulations, and Good Clinical Practice (GCP). In addition, the DSMC will regularly review serious adverse events and protocol deviations associated with the research to ensure the protection of human subjects. Results of the DSMC audit will be communicated to the IRB and the appropriate regulatory authorities at the time of continuing review, or in an expedited fashion, as needed.

10.2 Protocol Review and Amendments

The protocol, the proposed informed consent and all forms of participant information related to the study (e.g. advertisements used to recruit participants) will be reviewed and approved by the Stanford IRB and Stanford Cancer Center Scientific Review Committee (SRC). Any changes made to the protocol will be submitted as a modification and will be approved by the IRB prior to implementation. The Protocol Director will disseminate the protocol amendment information to all participating investigators.

10.3 Data management

Patient data/demographics will be kept in the RedCap clinical research database tool provided by Stanford University's Clinical Informatics department (clinicalinformatics.stanford.edu). Images are kept in the clinically supported and secured PACS system, until a researcher exports de-identified images for publication. Identified information will only be kept in either a secure clinical system or the secure RedCap database; all exported data will be de-identified.

10.4 Study Documentation

The Protocol Director, or her designee, will prepare and maintain adequate and accurate participant case histories with observations and other data pertinent to the study. Original source documents should be transcribed to Case Report Forms (CRFs) and used to analyze the study data. Source documents include hospital records, clinical charts, laboratory and pharmacy records, and recorded electronic data

11. STATISTICAL CONSIDERATIONS

11.1 Statistical Design

11.1.1 Randomization

Non Randomized

11.2 Primary Analysis

11.2.1 Analysis Population

All MR images of the study population will be included in the analysis. In case of missing data or non-adherence to protocol, the subject will be excluded from analysis.

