2.4 Study Design

Diagnostic: The goal of our project is to establish a novel, non-invasive, immediately clinically applicable imaging test for the differentiation of bone sarcomas (osteosarcomas and Ewing sarcomas) and osteomyelitis. Our approach relies on the FDA-approved iron supplement drug ferumoxytol (Feraheme), which is used in patients for intravenous treatment of iron deficiency. Ferumoxytol is composed of iron oxide nanoparticles, which provide a strong T1- and T2-signal on magnetic resonance (MR) images and, thus, can be used as an MR contrast agent. Based on our extensive experience with pre-clinical and clinical imaging applications of iron oxide nanoparticles, we hypothesize that MR image after intravenous injection of ferumoxytol will demonstrate a significantly stronger T1- and T2- enhancement of osteomyelitis when compared to malignant bone sarcomas.

Hypotheses:

(1) *Bone sarcomas and osteomyelitis show a different T1-enhancement at 1 h post injection (p.i.) of ferumoxytol*

(2) *Bone sarcomas and osteomyelitis demonstrate differences in T2-enhancement at 24 h p.i. of ferumoxytol*

We plan to enroll 20 patients in this study, 10 patients with bone sarcomas and 10 patients with an osteomyelitis. The sample size has been determined based on our preliminary data and power calculations. We will screen all patients with proven or suspected bone sarcoma or osteomyelitis for potential participation in this study. Inclusion criteria will comprise an age of 10-21 years (we do not include younger patients in order to exclude need of sedation) and a suspected or confirmed diagnosis of a bone sarcoma or osteomyelitis. Exclusion criteria comprise MR-incompatible metal implants, need of sedation (since an anesthesia is not supported by this), claustrophobia or hemosiderosis/hemochromatosis. All patients will undergo two subsequent imaging tests on a 3T MR scanner, using dedicated surface coils for high resolution MR imaging. During the first MR examination, ferumoxytol will be injected intravenously at a dose of 5 mg Fe/kg:

(A) MRI before and up to 1 h after injection of ferumoxytol for evaluation of lesion perfusion, blood volume, microvascular permeability and interstitial retention (enhanced permeability and retention effect of macromolecules)

(B) 24h after (A): Follow up MRI for evaluation of macrophage phagocytosis

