4. TREATMENT PLAN

STUDY PLAN:

All potential participants will be patients seen through regular referral methods in [name] clinic. During the course of a normal clinic visit, if [name] notes a patient who meets the inclusion/exclusion criteria, they will be offered an opportunity to enroll in the study.

We will screen all patients with proven or suspected bone sarcoma or osteomyelitis for potential participation in this study.

Following screening parameters will be recorded within 30 days prior to enrollment:

- i) Complete medical history
- ii) Physical Examination
- iii) Vital Signs
- iv) Height
- v) Weight
- vi) ECG

Once enrolled, each participant will undergo an initial MRI without contrast and with ferumoxytol injection for anatomic detailing, and then another MRI without contrast (delayed imaging) 24 hours later to assess the metabolic reaction to the contrast agent (macrophage phagocytosis, the difference in how the two different diseases react to the contrast agent).

Screening of the patient will take 15-30 minutes. Active participation involves two MRI scans for a total of approximately 2-3 hours. Data analysis will continue until publication in approximately 12 months from initiation of the study.

Audio recording, video recording and photography will not be used. Tissue samples will not be retained.

DRUG ADMINISTRATION:

The study requires one intravenous injection of Feraheme during the first MRI scan for diagnostic purpose, at a dose of 5 mg Fe/kg. Considering a Ferumoxytol/Feraheme dose of 5 mg/kg and a concentration of 30 mg Fe/ml, we anticipate to inject 250-400 mg Fe in a teenager with an average body weight of 50-80 kg. This will translate into 8.3 – 13.3 ml volume of contrast agent to be injected. An M.D. will administer the contrast agent slowly via a hand injection, with continuous and direct feedback from the patient, over a time period of 1-2 minutes, i.e. with a maximum injection rate of 10 ml / min. According to continuous feedback from the patient during the contrast media administration, we will inject slower as deemed appropriate.

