4.2 Criteria for Removal from Study

Criteria for removal from study:

- i) Incomplete MR images,
- ii) Image artifacts

- iii) Adverse reaction to contrast agent,
- iv) Upon request of Patient for exclusion from study
- v) Suspected patients of bone sarcoma or osteomyelitis with incorrect assignment to a pathology.

Patients removed from the study will be replaced in order to reach a total of 10 subjects for each pathology.

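### Section 11.2.1 excludes the whole patient for any missing data or non-adherence, so a missed 24 h scan or an unrelated deviation discards a valid 1 h T1 result

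*Combined protocol and SAP*

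**What the plan says.** Section 11.2.1 defines the only analysis population in the document. Its first sentence is general: "All MR images of the study population will be included in the analysis". Its second makes an exception: "In case of missing data or non-adherence to protocol, the subject will be excluded from analysis". The exception acts on the subject. It sets no threshold, does not define non-adherence, and is not tied to an image or an endpoint. Section 9.1.1 says that the outcome is measured in everyone included.

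Section 2.4 hypothesises that the two diseases "show a different T1-enhancement at 1 h post injection (p.i.) of ferumoxytol" and that they "demonstrate differences in T2-enhancement at 24 h p.i. of ferumoxytol". The first is read from exam A (before and up to 1 h after injection). The second is read from exam B, 24 h later, against the precontrast baseline. Section 4 fixes when exposure occurs: "The study requires one intravenous injection of Feraheme during the first MRI scan for diagnostic purpose".

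Section 4.2 lists five reasons for removal. The first is "Incomplete MR images" and the second is artifacts. It adds: "Patients removed from the study will be replaced in order to reach a total of 10 subjects for each pathology". Non-adherence is not one of the five reasons, and 11.2.1 does not mention replacement.

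**The concern.** The unit of exclusion is larger than the unit of missingness. The 1 h T1 value needs only exam A, so the absence of exam B does not invalidate it, yet the rule deletes it. The reverse also holds: a patient whose 1 h images fail but who has usable precontrast and 24 h images is lost to T2. Because non-adherence is undefined, a deviation with no bearing on the image can have the same effect.

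The study plans only 10 patients per disease, aged 10 to 21, each given an off-label injection before it is known whether the second scan will take place. Discarding a valid measurement from such a patient wastes information already obtained. It also weakens the estimates that section 11.2.2 calls key, the standard deviation and the coefficient of variation in each group.

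**Working it through.** **Inputs from the document.** 10 + 10 patients (11.3.1); 80% power at 1.33 SD, 18 degrees of freedom, and 30% and 4% chances of underestimating a future sample size by 20% and 50% (11.3.2).

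**Inputs assumed.** Two-sided alpha of 5%, since none is stated. Loss of 10 to 20%, since no dropout or missed-scan rate is given.

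**1. Reproduce the plan's figures.** For a two-sample t-test, noncentrality = 1.33/√(1/10 + 1/10) = 2.97 with 10 + 10 − 2 = 18 df. Power is 80.3%, and the difference detectable with 80% power is 1.325 SD. For the precision statement, P(χ²₁₈ < 0.8 × 18) = 29.7% and P(χ²₁₈ < 0.5 × 18) = 4.0%. All stated figures reproduce, and all presuppose 20 analysed patients.

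**2. Missed 24 h scan, replaced under 4.2.** A missed scan is naturally an incomplete image set, so the patient is removed and replaced. Expected injections to obtain 20 complete patients = 20/(1 − q), where q is the assumed proportion not completing:

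| q | Expected injections | Surplus |
|---|---|---|
| 10% | 20/0.90 = 22.2 | 2.2 |
| 15% | 20/0.85 = 23.5 | 3.5 |
| 20% | 20/0.80 = 25.0 | 5.0 |

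If non-completion means only a missed exam B, each surplus patient has a valid T1 exam that 11.2.1 discards. At q = 10%, the chance of at least one such patient among the first 20 is 1 − 0.9²⁰ = 88%. Power is unchanged.

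**3. Non-adherence alone, not replaced.** This trigger is in 11.2.1 but not in 4.2. If it removes 10, 15 or 20% of the 20 patients:

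| Analysed | df | Power at 1.33 SD | Detectable difference (80% power) | P(underestimate by 50%) |
|---|---|---|---|---|
| 10 + 10 | 18 | 80.3% | 1.325 SD | 4.0% |
| 9 + 9 | 16 | 75.5% | 1.41 SD | 5.1% |
| 9 + 8 | 15 | 72.5% | 1.46 SD | 5.8% |
| 8 + 8 | 14 | 69.7% | 1.51 SD | 6.5% |

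The t-test is used because it reproduces the plan's 80%. The planned Wilcoxon test, simulated on normal data with exact p-values, gives about 76%, 69% and 67% at 10, 9 and 8 per group.

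**4. With sets defined by endpoint.** A patient lacking only exam B stays in the T1 set. If that patient is still replaced for T2, T1 has on average 22.2, 23.5 or 25.0 patients at the three rates, and T2 has 20. If the only fault is a deviation that leaves the images valid, both sets keep the patient and the losses in step 3 do not occur.

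**The case against.** The strongest reply is that section 4.2 already protects the sample size. A reader might infer that missed 24 h scans push the study below 10 + 10 and erode its power. The document does not support that: an incomplete image set is a listed reason for removal, and removed patients are replaced. The power losses in step 3 apply only to exclusions outside the 4.2 list.

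A reader might also infer that changing 11.2.1 would spare replacement patients an injection. That does not follow. If 10 per disease are wanted for T2 at 24 h, a patient without that scan must still be replaced.

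Three further points stand. The two sentences of 11.2.1 can be read as a rule and its exception, so they need not contradict each other. The silence of 11.2.1 on replacement does not conflict with 4.2, which governs enrolment. And section 11.3.2 presents this as a proof-of-concept pilot, gives power only for the record, and says that no clinically relevant difference is known, so power is a soft yardstick here.

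It might also be argued that missing the second scan is related to illness or early surgery and so biases the T1 comparison. That is possible, but nothing in the document establishes it, and the point does not rest on it.

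None of this answers the core problem: the stated rule removes a valid T1 measurement because something else is missing or was done incorrectly.

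**Conclusion.** The point holds as a fault in the analysis-population rule; the plan's sample-size arithmetic is sound. Its consequence depends on the trigger. For a missed 24 h scan, the cost is discarded T1 data from about 2 to 5 already injected patients at an assumed 10 to 20% non-completion, with 10 + 10 maintained. For non-adherence alone, the cost is an apparently unreplaced loss: about 5 points of power at 9 per group and 11 at 8 per group, with a somewhat less reliable standard deviation for planning.

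This rests on reading a missed scan as an incomplete image set, on the assumed loss rates and alpha, and on 11.2.1 governing both endpoints. It sits under the primary analysis heading and says only analysis, but no other population is defined. How far undefined non-adherence reaches is also a matter of interpretation. A change is advisable, and it is cheap.

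**What to change.** Replace the second sentence of 11.2.1 with sets defined by endpoint:

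- **T1 set:** patients with a confirmed disease group who have not withdrawn from the study and have evaluable precontrast and 1 h T1 images.
- **T2 set:** the same, with evaluable precontrast and 24 h images.
- A deviation or artifact removes only the measurement it invalidates, decided without sight of the enhancement value or the diagnosis.

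Reconcile 4.2(i) and (ii) with this, so that one unusable exam does not remove the other. Leave (iv), removal at the patient's request, and (v), wrong assignment of a suspected case, in force. State also whether images from a patient removed under (iii) count; no proposal is made here on that criterion. Finally, state that the target of 10 per pathology is counted per endpoint, so that a patient kept for T1 may still be replaced for T2.

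The cost is a few sentences in 11.2.1 and 4.2. T1 and T2 may then have different numbers, to be reported side by side with the reasons for each exclusion. The change recovers T1 data; whether it reduces replacement injections depends on the T2 target.

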11.2.2 Analysis Plan

Descriptive statistics will be used to characterize contrast enhancement and relaxation times in both T1 and T2* settings, in each population; the key estimates will be the standard deviation and the coefficient of variation.

The area under the ROC curve will be calculated as a measure of separation and the significance of the separation will be assessed using the Wilcoxon rank sum test.

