2.5 Correlative Studies Background

Our group has worked on MR imaging techniques with iron oxide nanoparticles since 1995 (11-24). We and others have found that intravenously injected USPIO with diameters in the order of 20-50 nm cause a long lasting, positive “blood pool” or vascular enhancement on T1-weighted MR images (9,14,19). In pathologies with an increased microvascular permeability, USPIO extravasate into the interstitium and cause a T1-effect of

the target tissue, which is strongly dependent on the proton content of the interstitial space (among other technical factors). We have thoroughly investigated various factors that lead to an optimized tissue T1-enhancement of USPIO (9, 14, and 19). We have shown that malignant lesions in the bone marrow of patients show nearly no USPIO T1-enhancement, presumably due to their high cellularity, small intercellular space and low proton content (Fig. 1). Inflammations, on the other hand, show a strong T1-enhancement, presumably due to the edematous, proton rich environment (Fig. 2). These data suggest that tumors and inflammations may demonstrate differences in T1-enhancement.

USPIO in the interstitium are subsequently slowly phagocytosed by macrophages in various target tissues, such as liver, spleen, bone marrow or macrophage containing pathologies, where they primarily cause a negative (dark) signal effect on T2-weighted MR images (11,13,18,19,24). Focal malignant tumor lesions in organs of the RES (reticulo-endothelial system) contain no or very few macrophages, thus do not phagocytose USPIO, and stand out as bright lesions (Fig. 1). However, macrophage rich inflammations cause a marked signal loss on delayed T2-weighted MR images (Fig. 2). Thus, we have evidence from a variety of pre-clinical and clinical investigations, that tumors and inflammations may show distinct T2-enhancement patterns.

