6. DOSE MODIFICATIONS

Dose modification scheme:

- (A) Serious anaphylactoid reactions are not dose dependent. Thus, in case we should observe an increased incidence of severe anaphylactoid reactions, i.e. more than one patient in our limited study population of 20 patients, or if any of our patients encounters a permanent impairment due to the ferumoxytol administration, the study will be terminated.
- (B) In case we should observe an unexpected decrease in blood pressure of more than 10% in more than one patient via blood pressure measurements or in case we observe severe nausea in more than one patient, we will successively decrease the administered dose by 1 mg/kg until event-free tolerance is achieved. Of note, our colleagues from Oregon Health & Science University (see below) reported no such side effects of ferumoxytol in their population of children with brain tumors.
- (C) Precontrast MR scans will serve as an internal standard. We will measure the signal intensity of sarcomas and osteomyelitis and divide this signal by the signal of normal muscle to normalize for potential MR spectrometer variations over time. We expect at least 20% tumor/muscle enhancement on post-contrast T2-weighted MR scans compared to precontrast scans. If this enhancement will not be achieved, but ferumoxytol is well tolerated, we will increase the administered dose to 6 mg Fe/kg with a maximum total amount of 510 mg Fe (FDA-approved dose for single injection).

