9.1.3 Measurement Methods

Primary outcome of these examinations is to define distinctive MR signal characteristics of bone sarcomas and osteomyelitis, which will be immediately applicable in a clinical setting.

The MR signal intensity of the bone lesion, bone marrow, adjacent normal muscle, and background noise will be measured by operator defined regions of interest (ROI). The contrast enhancement of the bone lesions will be calculated as $(SI_{post}/SI_{pre})/SI_{pre} \times 100\%$. The bone marrow will serve as a positive internal standard to confirm contrast accumulation at the target site and muscle will serve as a negative standard (no enhancement expected). Serial signal-to-noise ratios of the lesion on dynamic postcontrast T1-SPGR sequences will be used to calculate the blood volume of the lesion and microvascular permeability of ferumoxytol via kinetic analyses as described previously.

9.1.4 Measurement Time Points:

Data analysis of the initial MR scan and 24hr Delayed MR scans will be performed

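### The coefficient of variation is a key estimate for contrast enhancement, but it can be uninterpretable where mean enhancement is near zero, chiefly sarcoma on T1

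*Combined protocol and SAP*

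**What the plan says.** Section 11.2.2 sets the scope: "Descriptive statistics will be used to characterize contrast enhancement and relaxation times in both T1 and T2* settings, in each population". It then adds that "the key estimates will be the standard deviation and the coefficient of variation". The synopsis repeats this for enhancement. No exception is made for enhancement as against relaxation times. The next sentence of section 11.2.2 adds the area under the ROC curve (AUC) and a Wilcoxon rank sum test.

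Section 2.5 gives the expected direction of the effects:

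- T1, tumour: "malignant lesions in the bone marrow of patients show nearly no USPIO T1-enhancement".
- T1, inflammation: "Inflammations, on the other hand, show a strong T1-enhancement".
- T2, inflammation: "macrophage rich inflammations cause a marked signal loss on delayed T2-weighted MR images".
- T2, tumour: focal malignant lesions "contain no or very few macrophages, thus do not phagocytose USPIO, and stand out as bright lesions".

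Section 6(C) gives a different picture for T2 in tumour: "We expect at least 20% tumor/muscle enhancement on post-contrast T2-weighted MR scans compared to precontrast scans". It does not state the sign.

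Section 9.1.3 prints enhancement as (SIpost/SIpre)/SIpre × 100%. Section 11.3.2 bases future sample-size planning on a pooled SD with 18 degrees of freedom.

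**The concern.** A CV needs a scale with a real zero and a mean well away from it. A percent change from baseline can be positive, zero or negative, and the background expects each of these somewhere in the study. Where the mean is close to zero, small sampling error in the mean makes the CV very large or reverses its sign.

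A second problem remains even when the CV is stable. The hypotheses in sections 1.1 and 2.4 are that enhancement differs between the two pathologies. If the means differ and the SDs are the same, the CVs must differ. The CV therefore cannot show whether one pathology is more variable than the other.

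At stake is one of the two designated key estimates for the primary outcome. Meanwhile the group means and their difference in percentage points, which a later study would need, are not named as key estimates.

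**Working it through.** **1. The plan's own figures.** These reproduce, and none uses the CV.

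- Power: two-sample t-test, 10 per group, difference 1.33 SD, noncentrality 1.33 × √(10/2), 18 df, two-sided alpha 0.05 (assumed; not stated). Result 80.3%, against the stated 80%.
- Underestimating a future sample size by 20%: P(χ² with 18 df < 18 × 0.8 = 14.4) = 29.7%, against 30%.
- Underestimating it by 50%: P(χ² with 18 df < 18 × 0.5 = 9) = 4.0%, against 4%.

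**2. What enhancement means.** The formula printed in section 9.1.3 is always positive and carries units of 1/signal. Take SIpre = 300 as an example:

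| SIpost | Printed formula | (SIpost − SIpre)/SIpre |
|---|---|---|
| 300 | 0.33% | 0% |
| 360 | 0.40% | +20% |
| 240 | 0.27% | −20% |

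Under the printed form an unchanged lesion scores 100/SIpre %, not zero. Elsewhere the protocol treats enhancement as a change with a true zero. Section 9.1.3 expects none in muscle, section 6(C) expects at least 20% relative to precontrast, and section 6(D) and study stopping rule (C) act on there being none. The signed-change reading fits these places; the printed formula does not. The rest of this check assumes the signed change.

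**3. Stability of the CV at n = 10.** The documents give no mean or SD of enhancement, so the true mean/SD ratio r is assumed over a range, with normal data. The chance that the sample mean, and so the CV, has the wrong sign is Φ(−|r|√10). At r = 0.25 this is Φ(−0.79) = 21%. The 95% ranges come from 400,000 simulated samples at each r.

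| r | True CV | Wrong sign | 95% range of sample CV |
|---|---|---|---|
| 0.25 | 4 | 21% | −34 to +37 |
| 0.5 | 2 | 5.7% | −11 to +16 |
| 1 | 1 | 0.08% | 0.46 to 2.69 |
| 2 | 0.5 | about 0 | 0.26 to 0.84 |
| 3 | 0.33 | about 0 | 0.18 to 0.52 |

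Negative means mirror these rows. At r = −2 the CV is about −0.5, with range −0.84 to −0.26: negative but stable. The sample SD stays within √(χ²/9), that is 0.55 to 1.45 times its true value, whatever the mean.

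**4. Comparing groups.** Take equal SDs and the plan's own difference of 1.33 SD. If sarcoma has r = 1, osteomyelitis has r = 2.33, and the CVs are 1/1 = 1.00 and 1/2.33 = 0.43. If sarcoma has r = 0.25, osteomyelitis has r = 1.58, and the CVs are 4.00 and 0.63. Variability is identical in both cases; only the means differ.

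**The case against.** The strongest reply is that little in the plan depends on the CV. The SD is also a key estimate and is sound. Relaxation times, covered by the same sentence, are strictly positive, so the CV is proper there. The AUC is a legitimate between-group measure for a diagnostic aim, and planning in section 11.3.2 uses the pooled SD. All of this stands. A reader might infer that the pilot cannot supply the variance for its next study, or that it has no measure of group separation. The documents support neither.

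The instability also rests on assumed ratios. The near-zero T1 evidence in section 2.5 comes from other marrow malignancy (Figure 1 shows lymphoma) and another agent, ferumoxtran-10. If sarcomas enhance little but uniformly, the SD may be small too and the ratio less extreme. If the 20% in section 6(C) held with an SD of 20 points, r would be 1 and a wrong sign would be rare. This stands against any claim that the CV will be unstable; it does not show that it will be stable.

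A reader might also infer that signal loss on T2 makes the CV unstable. It does not when the loss is marked: the CV is then negative but steady, and only a sign convention is missing. The near-zero risk on T2 lies in sarcoma, where sections 2.5 and 6(C) differ.

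Finally, the formula as printed cannot produce a zero or negative value. That is correct, but it conflicts with how the rest of the protocol uses the term, so it does not rescue the CV.

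**Conclusion.** The point holds in limited form. For signed percent enhancement, the CV can be unstable or of the wrong sign where the mean is near zero: chiefly sarcoma on T1, and possibly sarcoma on T2. It also cannot compare variability between pathologies whose means are hypothesised to differ. At n = 10 the trouble is serious at mean/SD ratios of about 0.5 or less and has gone by about 2. Which of these applies is unknown, because the documents give no mean or SD.

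The conclusion rests on the signed-change reading of enhancement and on roughly normal data. It does not extend to the SD, the AUC, the Wilcoxon test, the 18-df planning figures or the CV of relaxation times. It is worth correcting before analysis, since the CV is a designated key estimate for the primary outcome, but it does not undermine the design.

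**What to change.** In section 11.2.2 and the synopsis:

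- For percent enhancement, make the key estimates the group mean and SD in percentage points, and the between-pathology difference (mean difference or Hodges-Lehmann shift) with a 95% confidence interval, alongside the planned AUC. Section 11.3.2 says there is no information on a clinically relevant difference; an estimated difference with its interval would help a later study, which the AUC does not give in percentage points.
- Keep the CV only for strictly positive quantities such as relaxation times or the SIpost/SIpre ratio.

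In section 9.1.3, correct or clarify the enhancement formula and state whether T2 signal loss is reported as negative or as a positive magnitude. Sections 2.5 and 6(C) should be reconciled on the T2 effect expected in sarcoma, including its sign.

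The cost is a change of wording and a little more analysis. No new data are needed.
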